- 7) To minimize the risk of carry-over effects, we will exclude all prescriptions prescribed \leq 6 months after another prescription for a corticosteroid. Accordingly, the same patient can contribute data on several treatment courses, provided that there was $>$ 6 months since the last prescription was dispensed (See section 7 for justification for why a 6-month interval was chosen).
- 8) Duplicate prescriptions (same date, drug and dosage) will be kept in the analyses as a single treatment course. Cases of duplicate prescriptions on the same date, but where the drug or dosage is different will be excluded.

9) Baseline of the treatment course will be defined as the date when the prescription of either methylprednisolone or prednisolone was dispensed.

6. Emulated target trial matching procedure

In order to create balanced treatment groups and reduce the potential for confounding in the emulated study, we will apply a matching process for baseline characteristics including relevant comorbidities. Each methylprednisolone treatment course will be matched 1:1 with a prednisolone treatment course. The following characteristics will be matched for:

- Sex
- Age groups, defined as: < 45 years; 45 up to < 60 years; 60 up to < 75 years; 75 years or higher
- Equipotent dosage (4 mg methylprednisolone versus 5 mg prednisolone; 16 mg methylprednisolone versus 20 mg prednisolone). While prescription data from the NPD cannot provide the exact number of tablets of either medicine taken per day, we will assume that since the medications are taken by comparable populations and for comparable conditions, any differences will even out in this large dataset.
- Prescription groups based on ICD10 / ICPC2 refund codes:
 - i. Pulmonary
 - ii. Rheumatology and musculoskeletal
 - iii. Neurology and ophthalmology
 - iv. Dermatology
 - v. Endocrinology and metabolic
 - vi. Gastrointestinal
 - vii. Hematology and immunology
 - viii. Nephrology.
- Comorbidities as categorical variables (a. – e. defined as at least one ICD10 diagnosis code from a secondary or tertiary healthcare provider or at least one prescription of medication with relevant ICPC2 or ICD10 refund codes)
 - a. Atherosclerotic cardiovascular disease (coronary, cerebral and peripheral artery disease)
 - b. Chronic kidney disease
 - c. Diabetes (type 1 and 2)
 - d. Hypertension
 - e. Heart failure

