- Descriptive Statistics: The study will commence with descriptive statistics to provide an overview of baseline patient characteristics. This will include the calculation of means,

medians, standard deviations, and proportions to summarize key characteristics: Age, sex, comorbidities and glucocorticoid refund codes. Data will be presented in Table 1.

- *Primary and secondary outcomes*: We will employ appropriate statistical methods / survival analyses to assess the relationship between dichotomous treatment variables (methylprednisolone or prednisolone) and dichotomous outcomes of interest. These methods will be chosen based on the distribution and characteristics of the data, with consideration given to the matched nature of the study design and the requirements of each statistical test for valid results. Subgroup analyses will only be performed in the event of significant results in their respective primary and / or secondary outcome analyses. If manuscript formatting guidelines allow it, data will be presented in Figure 1 and 2. Sensitivity analyses including fatalities during follow-up will be presented in Figure 3.

- *E-value for sensitivity analyses*: To evaluate the robustness of our observed associations to potential unmeasured or residual confounding, we will calculate the E-value as described by VanderWeele and Ding (4).

- *Statistical Software*: The statistical analysis will be carried out using STATA MP16. A significance level of 0.05 will be used for all hypothesis tests.

12. Considerations about possible bias and limitations to the emulated target trial

Our emulated target trial will be subject to several sources of bias and potential limitations that merit consideration. First, the data we have is accurate only to the month and year, not to the exact date of events like prescriptions or diagnoses. This lack of precision can introduce temporal biases, particularly in the calculation of the duration between prescription dispensation and subsequent health outcomes. The imprecision in timing could either overestimate or underestimate the association between corticosteroid use and heart failure decompensation.

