Second, for the purpose of matching methylprednisolone and prednisolone prescriptions, we have categorized them into broad disease groups based on ICD10/ICPC2 refund codes. While this approach is necessary due to the nature of the available data, it introduces a level of generalization that might overlook nuances in patient diagnoses. The broad categorization may not perfectly align the severity or specific characteristics of the conditions being treated, which could affect the comparability between the two treatment groups.

Third, our data includes information about comorbidities, but lacks details regarding the severity of these conditions. This gap means we cannot fully account for the potential

impact of the severity of comorbidities on the outcomes of interest. It is plausible that more severe comorbid conditions could influence the choice of medication or affect the risk of heart failure decompensation independently of the corticosteroid used.

Fourth, in clinical practice, the choice between methylprednisolone and prednisolone might be influenced by the treating physician's perception of their relative efficacy, particularly in patients with heart failure. This selection bias could mean that methylprednisolone is preferentially prescribed to patients perceived to be at higher risk of heart failure decompensation, based on the hypothesis that it might be better. By calculating the E-value the reader will be able to evaluate themselves whether the likelihood that the observed differences were due to unmeasured confounding. Should the E-value be large, this would suggest that considerable unmeasured confounding would be required to negate the observed effect. Conversely, a small E-value would indicate that our results could be more susceptible to bias from unmeasured confounding. The E-value thus complements our 1:1 matching process and provides additional context for interpreting the possible impact of unmeasured variables on our study outcomes.

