This potential bias may be particularly problematic in cases where both the initiation of corticosteroid therapy and the outcome are recorded within the same calendar month. In such cases, it will be difficult to ascertain whether the heart failure event precipitated the corticosteroid prescription or, conversely, whether the corticosteroid use preceded and potentially contributed to the heart failure episode. However, we anticipate that this limitation may introduce a bias counter to our hypothesis, as clinicians are more likely to prescribe methylprednisolone to patients who have recently experienced an acute episode of decompensated heart failure under the belief that it may be safer or more beneficial in managing such patients. This prescribing tendency could result in a conservative bias in our findings, making it harder to detect a true protective effect of methylprednisolone, if one exists, in relation to heart failure decompensation.

Fifth, the definition of acute decompensated heart failure is complicated and ideally requires adjudication by experts with access to echocardiogram, biomarkers etc. By using ICD-10 codes there is a risk of both false positives and false negatives. However, we do not anticipate this bias to impact the treatment groups differently.

Recognizing these biases is crucial when interpreting our findings. If our analysis indicates that prednisolone is associated with less decompensated heart failure compared to methylprednisolone, this could be attributed to the biases mentioned. Conversely, should our results show that methylprednisolone is associated with lower rates of heart failure

decompensation, this would be particularly noteworthy. Such a finding would go against the expected bias in prescription patterns and could suggest a genuine difference in the impact of these medications on heart failure outcomes.

13. References:

2. Yao T-C, Huang Y-W, Chang S-M, Tsai S-Y, Wu AC, Tsai H-J. Association Between Oral Corticosteroid Bursts and Severe Adverse Events : A Nationwide Population-Based Cohort Study. *Ann Intern Med* 2020;173:325–330.

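### Heart failure is matched only as present or absent, although the plan expects recent decompensation to steer drug choice and already holds the records to adjust for it

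*SAP*

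**What the plan says.** Section 6 matches each methylprednisolone course 1:1 to a prednisolone course on sex, four age bands, equipotent tablet strength, eight refund-code groups and seven comorbidity items (a to g). Heart failure (item e) falls under the rule for items a to e: "defined as at least one ICD10 diagnosis code from a secondary or tertiary healthcare provider or at least one prescription of medication" with a relevant refund code. The only drug-use item is lipid-lowering treatment. Section 11 adds no covariate; its analysis statement is "We will employ appropriate statistical methods / survival analyses to assess the relationship" between treatment and outcome.

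Section 12 says three things that bear on this choice:

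- Severity is not available: "our data includes information about comorbidities, but lacks details regarding the severity of these conditions", and "more severe comorbid conditions could influence the choice of medication or affect the risk of heart failure decompensation independently" of the corticosteroid used.
- Selection may operate on perceived risk. It could be that "methylprednisolone is preferentially prescribed to patients perceived to be at higher risk of heart failure decompensation".
- Selection is expected to operate on recent events: "clinicians are more likely to prescribe methylprednisolone to patients who have recently experienced an acute episode of decompensated heart failure". This stands in a paragraph about cases where "both the initiation of corticosteroid therapy and the outcome are recorded within the same calendar month".

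The plan's answer is the E-value, plus the argument that the bias is conservative. Of a result favouring methylprednisolone it says: "Such a finding would go against the expected bias in prescription patterns".

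**The concern.** Under Section 6, a single heart failure code from January 2008 and an acute admission in the month before dispensing count the same. For a course dispensed in December 2017 these can lie up to 119 months apart (9 × 12 + 11). A recent acute decompensation is the same kind of event as the primary outcome, and Section 12 names it as a reason for choosing one drug over the other. Following the matching list exactly leaves that factor unbalanced.

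Three consequences follow.

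- **Estimates.** The whole-cohort estimate and, more strongly, the heart failure subgroup may carry confounding that could have been reduced.
- **Subgroups.** Section 11 runs subgroup analyses only after a significant result in the respective outcome analysis. If the bias pulls a real benefit towards no difference, the primary-outcome analysis in heart failure patients may never be run.
- **Interpretation.** Section 12 relies on the assumed direction of bias to give extra weight to a finding in favour of methylprednisolone. Nothing in the plan checks that direction, although the data to check it are held.

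**Working it through.** **Are the records held?** The plan states no figure to reproduce, so the first check sets its sections side by side.

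- Section 8 identifies acute contacts with a primary I50 diagnosis, and Section 4 dates records to the month. The same records before baseline give the time since the last acute contact.
- Section 9 counts new loop-diuretic prescriptions or dose increases. Neither can be defined without dispensing before baseline.
- Section 5, item 6, admits courses only from January 2010, with data from January 2008. Every course therefore has at least 24 months of look-back.
- Section 7 starts outcome counting in the month after dispensing. This settles the order of events but does not balance earlier decompensation between arms.

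**How large could the bias be?** All inputs below are assumptions; the SAP gives none.

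*Within heart failure.* Let p1 and p0 be the shares of methylprednisolone and prednisolone courses with a recent acute contact, and RR its risk ratio for the outcome. The bias factor is BF = (1 + p1(RR − 1)) / (1 + p0(RR − 1)). With p0 = 0.20:

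| p1 | RR = 3 | RR = 5 |
|---|---|---|
| 0.30 | 1.6/1.4 = 1.143 | 2.2/1.8 = 1.222 |
| 0.40 | 1.8/1.4 = 1.286 | 2.6/1.8 = 1.444 |

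*Whole cohort.* With s the share of prednisolone-arm events that occur in heart failure patients, W = 1 + s(BF − 1):

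| s | Lowest W (BF 1.143) | Highest W (BF 1.444) |
|---|---|---|
| 0.3 | 1.043 | 1.133 |
| 0.5 | 1.071 | 1.222 |
| 0.7 | 1.100 | 1.311 |

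A true risk ratio of 0.85 would appear as 0.85 × 1.043 = 0.886 up to 0.85 × 1.311 = 1.114. The benefit is erased at W = 1/0.85 = 1.176.

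*RMST scale.* Section 3 names RMST for the target trial; its use in the emulation is assumed here. For rare events the share of the gain kept is (1 − 0.85W)/0.15:

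- W = 1.043: 76% kept.
- W = 1.071 and 1.111 (s = 0.5, p1 = 0.30, RR 3 and 5): about 59% and 37% kept.
- W = 1.311: −76%, a reversed sign.

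A fuller calculation assumes a constant hazard within strata, a 1% six-month risk and heart failure in 10% of courses. It gives a true gain of about 0.14 days, observed as +0.104 to −0.109 days; the two middle cases keep 59% and 36%.

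*Loop diuretics alone.* With baseline use of 60% versus 50%, the factor within heart failure is 1.6/1.5 = 1.067 (RR 2) or 2.2/2.0 = 1.100 (RR 3). In the whole cohort it is 1.02 to 1.07.

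*Weaker imbalance.* With p1 = 0.25, p0 = 0.20 and RR = 2, BF = 1.25/1.20 = 1.042. W is then 1.013, 1.021 and 1.029 for s = 0.3, 0.5 and 0.7.

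*Opposite imbalance.* With p1 = 0.10 and p0 = 0.20, BF is 1.1/1.2 = 0.917 (RR 2) down to 1.4/1.8 = 0.778 (RR 5). At s = 0.5, RR 3 and RR 5 give W = 0.929 and 0.889. A true 0.85 would then appear as 0.79 or 0.76, an exaggerated benefit.

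**The case against.** The strongest reply is that the plan hides nothing. Section 12 discloses the missing severity detail and the likely selection, prespecifies the E-value and warns that a result favouring prednisolone could reflect these biases. Seven comorbidity items are matched and may absorb part of the imbalance. On this view, two more covariates are a matter of judgement. The disclosure is real, but it describes severity as unavailable without saying that two usable proxies are at hand. An E-value describes robustness to confounding; it does not remove confounding that can be measured.

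A second reply is that the sentence on recent decompensation belongs to the paragraph on same-month events, which the next-month rule already handles. The context is as described, but having recently had an episode is not confined to one calendar month. The separate statement on perceived risk has no time limit, though it is worded only as a possibility.

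Some points stand in part:

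- The magnitude rests wholly on chosen inputs. Near-null and opposite-direction results are possible, and the sign reversal needs the more extreme inputs in combination.
- Section 11's condition for subgroups also covers secondary outcomes. A non-significant primary result would block the primary-outcome subgroups, not necessarily all subgroup work.
- Section 5, item 6, can be read as fixing comorbidities in 2008–2009 only. The variable is still yes/no, and heart failure first recorded later would then be missed.

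**Conclusion.** The concern holds on the text. The plan names recent decompensation as a likely driver of drug choice, matches heart failure without regard to recency, and leaves out two proxies that its own outcome records supply. The conclusion does not depend on the illustrative numbers.

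The true size is unknown. Under the stronger assumed imbalances in the expected direction, the whole-cohort factor is 1.04 to 1.31 and the heart failure factor 1.14 to 1.44. Slight imbalance would make it negligible, and reversed imbalance would inflate the apparent benefit. That uncertainty over direction is itself a reason to measure the balance. The change should be made before analysis: it reduces bias at small cost, though it will not remove all confounding by severity.

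**What to change.** Prespecify two baseline covariates in Sections 6 and 11. Enter them in an outcome model on the matched set, standardised to the marginal effect (RMST or risk difference), or use them as matching factors.

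1. **Last acute contact with primary I50**, in a fixed 24-month look-back ending the month before dispensing: 1–3, 4–12 or 13–24 months ago, or none. For a January 2010 course this window is exactly January 2008 to December 2009, so the categories mean the same in every calendar year. The cut-points are a proposal.
2. **Any loop-diuretic dispensing** in the 6 months before the dispensing month.

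Keep contacts in the dispensing month out of the primary model, because they may follow dispensing. Report them by arm, and run a sensitivity analysis with and without those courses. Report standardised differences for both covariates by arm and use them to test the direction of bias assumed in Section 12. Amend the severity limitation there to say that these proxies exist and are used. Keep the E-value for what remains unmeasured.

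The cost is SAP wording, two derived variables from registries already in use, and four extra model parameters (three for recency, one for loop diuretics). Exact matching instead would lose some pairs. The nominal grid is 2 × 4 × 2 × 8 × 2^7 = 16,384 cells. With loop diuretics for all courses and recency only within heart failure, it becomes 8,192 × 2 + 8,192 × 4 × 2 = 81,920, about five times as many. The outcome model is therefore the cheaper route.

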The registry is approved by the Norwegian General Data Protection Regulation (16/00482-11/CDG), the South East Norway Health Authority Ethical Committee (2016/588), and the Data Protection Officers at Oslo University Hospital (2016/924) and Diakonhjemmet Hospital (7/12–2019). The NCRR comprises routinely recorded administrative data, and written consent from study subjects was not required.

For this study, we will use data from three key sources: The Norwegian Prescription Registry (NPD) serves as the foundation for prescription data, The Norwegian Patient Registry (NPR) provides diagnosis data, and data regarding age and sex are extracted from Statistics Norway (SSB). The data from these registers provide accuracy up to the month and year, but not to the exact date of events, like prescriptions or diagnoses.

5. Data preparation and eligible treatment periods in the target trial emulation

To maintain comparability between the methylprednisolone and prednisolone treatment groups in the emulated study, we will apply several data management steps:

- 1) Individuals aged \leq 18 years in January 2008 will be excluded
- 2) Analyses will be restricted to tablets, as prednisolone is only available in this form.
- 3) To allow for equipotent dose comparisons, we will focus only on 4 mg and 16 mg methylprednisolone and their counterparts in prednisolone at 5 mg and 20 mg, respectively. Patients with other doses will be excluded.
- 4) To facilitate comparisons of treatments prescribed for similar conditions, we will only include prescriptions with an International Classification of Diseases, 10th Edition (ICD10) or International Classification of Primary Care, 2nd Edition (ICPC2) refund code.
- 5) Patients with prescriptions for diagnosis codes including palliative care, cancer symptoms, medical complications, and organ transplants will be excluded. This exclusion aims to reduce the inherent heterogeneity within these groups, allowing for a more comparable baseline risk.
- 6) An initial 2-year observational period, spanning from January 2008 to December 2009, will be used to establish comorbidities. Accordingly, only prescriptions of methylprednisolone or prednisolone dispensed from January 2010, onward, will be eligible for analyses.

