- f. Chronic obstructive pulmonary disease, defined as at least one diagnosis code from a secondary or tertiary healthcare provider (not medication, as this is not included in the dataset).
- g. Use of lipid-lowering drugs, defined as at least one prescription of lipid-lowering drugs

7. Defining time intervals for outcome measurement and new treatment courses in the emulated target trial

Data on the temporal relationships between corticosteroid therapy and heart failure decompensation are scarce. A previous nested case-control study by Souverein *et al.* found that current use of oral corticosteroids was associated with an increased risk of heart failure (adjusted OR 2.66 [CI 2.46 to 2.87]) (1). This risk was considerably higher than among patients with recent (corticosteroid prescription last 3 to 12 months) and past (corticosteroid prescription last > 12 months) corticosteroid use (adjusted OR 1.40 [CI 1.27 to 1.55] and 1.19 [CI 1.08 to 1.32], respectively). Moreover, the association was stronger in the group with higher doses, although the dose-response relation was not continuous. However, no clear association with cumulative dose was observed. Later, a Taiwanese nationwide population-based study evaluating the effect of corticosteroid bursts (≤ 14 days treatment) in patients with heart failure also found that the risk was highest (incidence rate ratio 2.37 [CI 2.13 to 2.63]) during the first 5 to 30 days after treatment initiation, and considerably attenuated (incidence rate ratio 1.35 [CI 1.24 to 1.47]) during days 31 to 90 (2).

We must also consider the granularity of our data, which is limited to months and not days. For instance, a prescription recorded in January and an event in June could be 6 months apart (from Jan 1st to June 30th), but it could also effectively be 4 months apart (from Jan 31st to June 1st). Based on these considerations, we reason that 6-month intervals will provide a balanced period for observing medication effects on outcomes.

Due to the low granularity of our time data (limited to months and not days), the outcomes will be recorded from the first day of the month after the corticosteroid prescription. This is to make sure that the temporal relationship is in order and avoid cases where the corticosteroid prescriptions were dispensed after the outcomes.

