Our understanding of potential carry-over effects from one corticosteroid treatment course to another is limited. Thus, the ideal approach for our study would involve analyzing only the first instance of corticosteroid therapy to avoid such effects. However, since our dataset begins in January 2008, tracking the initial therapy instance for each patient is not

feasible. Given the findings of Souverein *et al.* that the cumulative corticosteroid dose was not associated with heart failure, and considering that the risk did not significantly increase between months 3 and 12 compared to after 12 months, we believe that a prescription dispensed ≥ 6 months after the last one provides a sufficient buffer. This approach ensures minimal residual effects from the previous treatment within the constraints of our dataset.

8. Primary outcome in the emulated target trial

The primary outcome of interest is an acute hospital contact (secondary or tertiary healthcare facilities) where the patient was given a primary diagnosis code for heart failure (ICD10 code i50*) at discharge. As discussed in section 7, the outcome will be assessed from the first day of the month after the corticosteroid prescription was dispensed and the following 5 months. This window will not be extended in cases where subsequent prescriptions for the corticosteroid is made so that the treatment course is longer than 6 months.

9. Secondary outcomes in the emulated target trial

Three secondary outcomes will complement the primary analysis. As for the primary outcome, we will investigate outcomes occurring during the first 6 months following the prescription of methylprednisolone or prednisolone. The secondary outcomes are as follows:

1. Any contact (acute or elective) with secondary or tertiary healthcare facilities where a primary diagnosis of heart failure is recorded
2. Initiation of newly prescribed loop diuretics or any increase in doses within the first 6 months after the prescription of methylprednisolone or prednisolone.
3. A combination of secondary outcome 1. and 2.

10. Subgroup analyses in the emulated target trial

The primary and secondary outcomes will be analyzed for the study population as a whole and within the following subgroups:

1. Only individuals with existing heart failure
2. Only individuals with existing heart failure or established ASCVD
3. Only individuals with at least 3 comorbidities (a. to g.)

11. Statistical analysis in the in the emulated target trial

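### COPD is identified from hospital codes only, although the refund code required on every eligible corticosteroid course could also reveal it

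*SAP*

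**What the plan says.** Section 6 gives two rules for establishing comorbidities before matching.

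- For a to e (atherosclerotic disease, kidney disease, diabetes, hypertension, heart failure), a specialist-care diagnosis is enough, "or at least one prescription of medication with relevant ICPC2 or ICD10 refund codes".
- COPD (item f) is "defined as at least one diagnosis code from a secondary or tertiary healthcare provider (not medication, as this is not included in the dataset").

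Three other places show that the diagnosis behind each corticosteroid course is held.

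- Section 5, item 4: "we will only include prescriptions with an International Classification of Diseases, 10th Edition (ICD10) or International Classification of Primary Care, 2nd Edition (ICPC2) refund code".
- Section 6 matches on "Prescription groups based on ICD10 / ICPC2 refund codes"; the first of the eight groups is Pulmonary.
- Section 11 lists the baseline characteristics to be summarised as "Age, sex, comorbidities and glucocorticoid refund codes".

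Item f has a second use. Section 10 defines its third subgroup as "Only individuals with at least 3 comorbidities (a. to g".).

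**The concern.** The sponsor chose COPD as a matching variable, so it already regards imbalance in COPD as worth removing. Yet the rule for finding COPD is narrower than the rule for a to e, and it passes over a source that the entry criteria guarantee. A patient managed outside hospital whose index steroid was refunded for COPD would be recorded as having no COPD. Matching on refund group keeps that course within Pulmonary, but the partner may have asthma or another lung disease with a different risk of heart failure admission.

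Two things are at stake: residual confounding that held data could reduce, and the membership of the subgroup with three or more comorbidities.

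**Working it through.** The plan gives no figure on this point to reproduce. The check compares the definitions and then illustrates the possible size.

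**Definitions side by side** (a hospital code means a secondary or tertiary care diagnosis code)

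| Variable | Hospital code | Refund code on a prescription |
|---|---|---|
| a to e | counts | counts |
| f, COPD | counts | does not count |
| Corticosteroid indication | not used | required for entry; matched in eight broad groups |

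Take a course with a COPD refund code in a patient with no hospital COPD code. It enters under section 5, item 4, falls in the Pulmonary group, and is set to no COPD under item f. Its partner must be Pulmonary and also recorded without COPD, but need not have COPD.

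Section 5, item 5 excludes certain prescriptions by diagnosis code (palliative care and organ transplant, for example). This suggests that the codes can be read below the level of the eight groups.

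**Size within the affected cells** (all inputs assumed; none is in the SAP)

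Let r be the risk ratio of COPD for the outcome, and let a and b be the hidden COPD shares among methylprednisolone and prednisolone courses in Pulmonary cells recorded without COPD. The spurious ratio is [1 + a(r − 1)] / [1 + b(r − 1)].

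- r = 2, a = 0.30, b = 0.25: 1.30/1.25 = 1.04.
- r = 2, a = 0.40, b = 0.25: 1.40/1.25 = 1.12.
- a = b: exactly 1.00 for any r.
- Shares reversed between the drugs: 1.25/1.30 = 0.96 and 1.25/1.40 = 0.89. The SAP does not settle the direction.

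**A second route to the hidden shares.** Let p be the true COPD share among Pulmonary courses and s the sensitivity of hospital codes, with no false positives. The hidden share among courses recorded without COPD is p(1 − s)/(1 − ps).

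- p = 0.5, s = 0.4: 0.30/0.80 = 0.375. With s = 0.8: 0.10/0.60 = 0.167. So 17% to 38% of these courses would be mislabelled, without bias if both arms are alike.
- p = 0.5 against 0.4, s from 0.4 to 0.8, r from 1.5 to 3: spurious ratio 1.02 to 1.11. At the upper end the hidden shares are 0.375 and 0.286, giving 1.750/1.571 = 1.11.
- p = 0.6 against 0.4, same ranges: 1.05 to 1.24. At the upper end the hidden shares are 0.474 and 0.286, giving 1.947/1.571 = 1.24.
- s = 1: hidden share 0, ratio 1.00 throughout.

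**Dilution in the pooled analysis.** If the affected cells gave 20% of expected events (assumed), ratios of 1.04 and 1.12 become about 1 + 0.20 × 0.04 = 1.01 and 1 + 0.20 × 0.12 = 1.02.

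**Subgroup 3.** Missed COPD removes a patient only if exactly two other listed comorbidities are recorded. Because pairs are matched on each recorded comorbidity, both members are counted in or out together. The subgroup shrinks, but the balance of the pairs that remain is not disturbed by the loss.

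**The case against.** A reader might infer that the SAP contradicts itself by saying medication is absent while requiring refund-coded prescriptions. The text does not support that. The parenthesis in item f most naturally refers to COPD drugs, such as inhalers, and gives an honest data limit. What remains is an unused source and a rule inconsistent with a to e.

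A reader might also infer that COPD patients will certainly be mislabelled. The SAP lists no individual refund codes. That COPD codes are among the Pulmonary ones is a reasonable inference, and the number of such courses without a hospital code is unknown.

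The harm is also limited by design. Pairs share refund group, sex, age group, dose and the other listed comorbidities, so any COPD risk ratio would have to persist after that matching. Section 12 concedes of the broad groups that "it introduces a level of generalization that might overlook nuances in patient diagnoses", and an E-value is planned for residual confounding. If the hidden COPD sits more in the methylprednisolone arm, the bias runs against the study hypothesis, as section 12 expects of preferential prescribing.

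These arguments reduce the likely size. They do not remove the point: section 12 does not mention missed COPD, and neither a caveat nor an E-value replaces a code that is already held.

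A last stronger reading is that subgroup 3 would be biased by losing patients. It would not, for the reason shown in the working. Section 11 also allows subgroup analyses only after a significant result in the corresponding main analysis.

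**Conclusion.** The point stands as an inexpensive improvement to the control of a confounder the sponsor itself selected. It is not an error that undermines the analysis. It depends on COPD codes occurring among the eligible refund codes, and on some of those patients having no hospital COPD code. Confounding further requires that the hidden share differ between the drugs.

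The illustrative ratios of 1.04 to 1.12 rest wholly on assumed inputs and apply only to Pulmonary cells recorded without COPD. The pooled effect would be smaller, by an amount the SAP does not allow one to calculate. For subgroup 3, the consequence is fewer eligible pairs.

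**What to change.** Redefine item f so that COPD is present with either a COPD diagnosis code from secondary or tertiary care, or a COPD refund code (ICD10 or ICPC2) on the index or any earlier corticosteroid prescription. Use this one definition for matching and for subgroup 3. The index code is fixed at dispensing and outcomes count only from the following month (section 7), so no post-baseline information enters.

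Add a sentence to section 12: COPD managed in primary care remains missed in patients never given a corticosteroid for COPD, so ascertainment depends partly on indication. That is the small downside of the change. If no COPD refund code occurs among eligible courses, one sentence saying so closes the point.

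The cost is a change of SAP wording and one derived variable from codes already held. No new data are needed.
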